1.0 OBJECTIVES AND SCIENTIFIC AIMS

Primary Objectives: In patients with high anxiety undergoing THA or TKA:

- 1) Determine if preoperative acupuncture reduces preoperative anxiety in the acupuncture group.
- 2) Examine postoperative pain following acupuncture compared to control.

Secondary Objective: To determine the safety of preoperative acupuncture by recording complications throughout hospital length of stay; to determine whether preoperative acupuncture reduces postoperative nausea and vomiting, reduces postoperative opioid consumption, reduces anxiolytics need during hospitalization and improves satisfaction compared to control in high-anxiety patients undergoing THA or TKA.

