4.2. Subject Exclusion Criteria

- Unable to give consent
- Uncontrolled diabetes (HbA1c \geq 8.0%)
- Infection at any of the acupuncture points
- Known allergy to metals
- Abnormal laboratory blood work values (INR >1.5, if available; platelet count <70,000, if available)
- Patients with active ongoing coagulopathy based on lab data (INR >1.5) and/or on current anticoagulant use which increases bleeding risk.
- Women in reproductive age or under the age of 52 years old, as acupuncture is not recommended with pregnancy
- Non-English speaking
- Revision TKA or THA

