6.0 PRETREATMENT EVALUATION

Baseline preoperative history and physical exam evaluations from the PREPARE clinic of the Bone-and-Joint Institute will be used to collect the clinical demographic variables listed below. Laboratory tests, shown below, are also recommended, and corresponding results will be gathered if they occurred within 60 days prior to surgery.

Clinical Demographic Variables of Interest

- Age
- Gender
- Race and ethnicity
- BMI
- History of bleeding disorders
- History of coagulopathy
- History of acupuncture treatment
- Uncontrolled diabetes mellitus
- Present infection at the sites of acupuncture
- History of mental illness
- History of TKA or THA surgery
- Known allergy to metal

- INR (if available)
- Platelet count (if available)

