7.0 INTERVENTION ORDER OF EVENTS

7.1 Acupuncture Group

1. On the day of surgery and prior to procedure, study patients will be waiting in the preoperative area.
2. The patient will be placed in bay #1 or other bay if #1 is not available in the preoperative area.
3. A member of the study personnel will assess the patient's baseline anxiety and pain.
4. The assigned acupuncturist will conduct a preoperative medical assessment and chart review on the patient prior to intervention.
5. The patient will then undergo the acupuncture procedure given by the assigned acupuncturist.
6. Anxiety and pain will be reassessed by a member of the study personnel after the procedure.
7. The patient will undergo their surgical procedure.
8. The patient will be reevaluated for pain three times; when they arrive to the post-anesthesia recovery unit (PACU), after an hour, and after 3 hours.
9. The patient will be reevaluated for PONV/Impact score two times; after an hour from their arrival to the post-anesthesia recovery unit (PACU), and after 3 hours. Postoperative antiemetics used will also be collected from the patient's chart retrospectively, following enrollment.
10. Postoperative opioid consumption and anxiolytics used throughout hospitalization will be collected from the patient's chart retrospectively, following enrollment.
11. Admission and discharge dates & times will be collected directly from the patient's chart retrospectively, following enrollment and used to determine total hospital length of stay.
12. Patient satisfaction regarding surgery will be evaluated within a week after the discharge from the hospital.

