8.0 OUTCOME EVALUATION

All outcomes will be measured during the time periods illustrated in Table 1 using the following measurement methods:

- PreOP anxiety: Amsterdam Preoperative Anxiety and Information Scale (APAIS; Appendix I)
- State anxiety: Visual Analogue Score (VAS; Appendix VI) will be compared between pre and post acupuncture in the same patient within the acupuncture group.
- State anxiety: Visual Analogue Score (VAS; Appendix VI) preop anxiety assessment will be compared between the two groups to assess their baseline preop anxiety status on day of surgery.
- Pain: 11-point Numeric Pain Rating Scale (NPS; Appendix V) will be compared between the two groups
- Postoperative opioid consumption: collected through EPIC and converted into morphine milligram equivalents (MMEs) using Appendix IV. This will be compared between the two groups. Postoperative nausea and vomiting (PONV): PONV impact score (Appendix VII) will be compared between the two groups. Additionally, postoperative antiemetics needed during hospital admission will be collected directly from EPIC and compared between the two groups.
- Satisfaction with surgery: questionnaire (Appendix III) provided by a member of the study personnel by phone within a week after the discharge from the hospital.
- Adverse events related to the interventions will be recorded throughout enrollment.
- Anxiolytics medication needed throughout hospitalization will be collected directly from EPIC and compared between the two groups.
- Hospital length of stay will be collected directly from EPIC using hospital admission and discharge dates & times; this will be compared between the two groups.

Table 1. Outcome measurement time, researcher-to-patient interface, and method for all study outcomes.

[figure not shown]
Time	Interface	Outcome/ Measurement (Acupuncture)	Outcome/ Measurement (Control)
-10 to -7 days	PREPARE Center	
 • Preoperative anxiety/APAIS 	
 • Preoperative anxiety/APAIS

HHC-IRB
 IRB NUMBER: HHC-2021-0348
 IRB APPROVAL DATE: 06/02/2023

PreAQ/PreOP	Holding bay	
 • Anxiety/VAS • Pain/NPS • Anxiolytics 	
 • Anxiety/VAS • Pain/VAS • Anxiolytics
PostAQ/PreOP	Holding bay	
 • Anxiety/VAS • Pain/NPS 	NA

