Patient demographic and clinical (including operative) characteristics will be compared between groups using an independent samples t-test if continuous data are normally distributed), or Mann Whitney U if continuous data are not normally distributed. A chi-square or Fisher's exact test (if cell counts are <5) will be used to compare these characteristics between groups for categorical variables. All continuous variables will be expressed as mean±SD or median, IQR as appropriate. Categorical variables will be expressed as frequency (%).

The primary and secondary study outcomes will be compared between groups two ways. First, an independent samples t-test or Mann Whitney U test if deemed more appropriate for the scale data (which may be considered ordinal) will be used to compare outcomes at each time point between the two groups. Second, a mixed model for repeated measures will be used to compare the study outcomes that are repeated over time (e.g., Pain). This model was chosen instead of a repeated measures ANOVA due to the ordinal nature of the repeated outcome measures in addition to this test being more appropriate for non-normal residuals, missing data, as well as the ability to treat the time points as discrete categories or as true numbers, which accounts for any variability in when the measures are administered to patients.

We anticipate that the timing of the measures being administered may fluctuate slightly due to measures being taken PostOP.

All analyses will be conducted using SPSS version 26.0. P (2-sided) < .05 will be deemed the level of statistical significance.

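### Opioid use before admission is not listed for collection and not adjusted for, so the MME comparison carries avoidable noise and chance imbalance that one chart field and a prespecified covariate would reduce

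*Combined protocol and SAP*

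**What the plan says.** The secondary objectives in section 1.0 ask whether acupuncture "reduces postoperative opioid consumption, reduces anxiolytics need during hospitalization and improves satisfaction compared to control". The outcome is defined in 8.0: "Postoperative opioid consumption: collected through EPIC and converted into morphine milligram equivalents (MMEs) using Appendix IV". Section 7.1 gives the window, and 7.2 repeats it for the control arm: "Postoperative opioid consumption and anxiolytics used throughout hospitalization will be collected from the patient's chart retrospectively, following enrollment". Table 1 lists opioid MME once, as a chart-review item up to discharge.

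Section 6.0 says that the clinic's preoperative history and examination "will be used to collect the clinical demographic variables listed below". That list, headed "Clinical Demographic Variables of Interest", has 14 items. It includes "History of acupuncture treatment", mental illness and earlier joint replacement, but no opioid or other analgesic use. The only current medication that section 4.2 excludes is described as "on current anticoagulant use which increases bleeding risk". Section 3.2 describes a simple 0/1 generator without strata or blocks.

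Section 11.0 compares outcomes between arms by "an independent samples t-test or Mann Whitney U test if deemed more appropriate for the scale data". The mixed model in the same section is for outcomes repeated over time, which total MME is not, and it names no covariates.

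**The concern.** A patient who takes opioids at home for joint pain is likely to keep taking them in hospital. Those doses then count as postoperative consumption, although one preoperative acupuncture session would not be expected to remove them. If home users are a visible minority and take clearly more than the rest, they account for a sizeable part of the variation in MME. With about 30 per arm and no stratification, their number can also differ between arms by chance, and such a gap can mimic or hide an opioid-sparing effect. If the field is never recorded, nobody reading the result can tell whether that happened. What is at stake is the precision and interpretability of one named secondary outcome.

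**Working it through.** **The plan's own figure.** Section 11.0 gives no power for MME. Its governing calculation is for pain: N = 52, effect size f = 0.40319, 5% level, 81% power. With λ = 52 × 0.40319² = 8.45 and an F test on 1 and 50 degrees of freedom, I get 81.4%, so it reproduces. Attrition: 52/0.9 = 57.8, so 58; the target is 60. I use 30 × 0.9 = 27 evaluable patients per arm.

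**Chance imbalance.** Take 30 per arm and an assumed 20% home users. The difference in counts has SD √(2 × 30 × 0.2 × 0.8) = 3.1. For two independent Binomial(30, 0.2) counts, P(|difference| ≥ 4) = 0.256. If users take twice the usual dose, a gap of 4 shifts the mean difference by (4/30) × (2 − 1) = 13% of the non-user mean, against an assumed true effect of 30%.

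**Inputs for power.** All are assumptions. The two opioid trials with figures in section 2.0 give reductions of 1 − 37/54 = 31% and 1 − 620.7/868.6 = 29%, and CVs of 18/37 = 0.49, 21/54 = 0.39, 258.2/620.7 = 0.42 and 319.3/868.6 = 0.37. I take a 30% reduction and CV 0.4, with CV 0.8 as a wider case. The home-user share p and dose ratio m are not in the documents.

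**Hand calculation on the log scale.** MME is taken as lognormal and the reduction as proportional.
- Effect: |ln 0.7| = 0.357.
- Residual variance: ln(1 + CV²), which is 0.148 at CV 0.4 and 0.495 at CV 0.8.
- Variance added by home users: p(1 − p)(ln m)².
- Share of variance explained by home use: R² = added / (added + residual).
- Approximate power: Φ(0.357 / [SD × √(2/27)] − 1.96).

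For CV 0.4 with 20% users at 2 times, the added variance is 0.16 × 0.480 = 0.077 and the total is 0.225, so SD = 0.475 and R² = 0.34. Unadjusted power is Φ(2.76 − 1.96) = 79%. With home use adjusted for, SD = 0.385 and power is Φ(3.40 − 1.96) = 93%.

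**Simulation.** 27 per arm, no zero-MME patients; repeated runs agree within about 2 points.

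| Setting | R² by hand | Unadjusted log test by hand | Mann Whitney, simulated | Rank model adjusted for home use, simulated |
|---|---|---|---|---|
| CV 0.4, 10% users at 1.5 times | 0.09 | 90% | 88% | 91% |
| CV 0.4, 20% users at 2 times | 0.34 | 79% | 76% | 89% |
| CV 0.4, 30% users at 3 times | 0.63 | 54% | 54% | 88% |
| CV 0.8, 20% users at 2 times | 0.13 | 41% | 39% | 44% |

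With no home users at CV 0.4, Mann Whitney power is about 90%. At CV 0.4 the gain comes from the covariate and not from the scale: with 20% users at 2 times, a simulated log t-test without the covariate reaches only 76%.

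**Zeros.** Suppose 5% of non-users have zero MME: 0.05 × 0.8 × 54 ≈ 2 patients. Assume also a mean of 60 MME, CV 0.4 and 20% users at 2 times. Power is then 68% for the planned Mann Whitney, 38% for an adjusted model of log(MME+1), and 84% for the adjusted rank model. The reason is simple: on the log(MME+1) scale a zero lies about 4.0 below the typical control value, roughly ten residual SDs of 0.385.

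**The case against.** The case for leaving the plan alone is that the comparison is unbiased, the outcome is secondary, no power is claimed for it, and the Mann Whitney option already blunts the effect of heavy users. All of that is true. It limits the weight of the point, but it does not explain why a cheap prognostic field should be left out.

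The inputs are also weak. The cited reductions and CVs are for intraoperative doses against sham, whereas this trial measures postoperative MME against no intervention. They serve only as illustration. If home users are few and take only 1.5 times as much, the loss is about 3 points.

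A reader might infer that one chart field would restore full power. The documents do not support that. At CV 0.8 the comparison stays badly underpowered either way. If home doses simply add on and are untouched by treatment, adjusted log-scale power at CV 0.4 was 80-91% in simulation, so full recovery is not assured.

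A reader might also reach for an adjusted log(MME+1) model as the main analysis. The documents give no rate of zero-MME patients, and about two among 54 would be enough to put that model below the planned test.

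Finally, the appendices are not in the text, and 11.0 speaks of clinical and operative characteristics in general, so the list in 6.0 may not be exhaustive. A field on an unseen form cannot be ruled out. Even so, no section names one, and 11.0 as written would not use it.

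**Conclusion.** The point holds as a matter of precision and chance imbalance in a secondary outcome. Pre-admission opioid use is not listed, excluded, stratified or adjusted for anywhere in the text.

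Its size cannot be fixed from the documents. It ranges from nothing, if there are no home users, through about 3 points (few users, modest doses) to about 34 points (88% against 54%, with 30% of patients taking three times as much). The upper end needs CV 0.4, a 30% reduction and no zero-MME patients. The 26% chance of a gap of 4 or more users needs only the assumed 20% share and arms of 30, which simple randomisation does not guarantee.

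A reader might infer systematic bias in favour of one arm, or a threat to the primary outcomes. Neither follows: allocation is random, and the sample size rests on pain. The change is worth making because it is cheap and because adjustment costs almost nothing if home use turns out to be rare.

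**What to change.** In 6.0, add opioid use before admission (yes/no, and daily MME from the EPIC home-medication list) for all patients, including those already enrolled. Take it as recorded at the PREPARE visit, so that it predates randomisation.

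In 11.0, before any comparison of MME between arms, prespecify the main MME analysis as one that adjusts for this field and tolerates zeros. A linear model of ranked MME on arm and pre-admission opioid use would do, as would a van Elteren (stratified Mann Whitney) test by pre-admission use. Keep the unadjusted Mann Whitney U as a check. Do not make log(MME+1) the main model.

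The cost is one field in a chart that study staff already review, a short addition to 11.0 and one degree of freedom. A rank-based result does not give an effect in MME, so report medians by arm or an adjusted mean difference beside it. Eligibility, treatment and visits do not change.

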9.2 Data and Safety Monitoring

The study investigators will be responsible for the safety of the study participants, and they will stress the importance of reporting adverse events to the participants. Investigators will also consistently monitor each participant for adverse events. Adverse events, related or unrelated to the acupuncture procedure, will be reported, attributed, and graded for severity by the clinician and documented in EPIC. Serious adverse events or unanticipated problems will be reported to the IRB.

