10.2 Adverse Events

The incidence and severity of adverse events is highly dependent on the experience and skill of the practitioner, and when provided by a physician, acupuncture is accepted as a safe treatment.^[29,36,37] Acupuncture-related adverse events occur in about 6% of cases; the vast majority of these are usually minor and most commonly include bleeding, discomfort, and residual pain at the insertion points.^[36] Serious acupuncture-related adverse events occur in just 0.024% of cases.^[37] Of these, the most frequently cited include: pneumothorax, abdominal injuries, heart injuries, CNS injuries, neck injuries, eye injuries, peripheral nerve injuries, and infection.^[37] Though acupuncture-related deaths have been reported, the incidence is statistically negligible, and even surveys covering more than 3 million acupuncture treatments report no cases of death.^[38]

Adverse events will be monitored during and after acupuncture and throughout admission. Events will be recorded as safety measures. Emergency visits and hospital readmissions stated in EPIC will be recorded up to thirty days postoperatively.

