10.3 Serious Adverse Event (SAE) Reporting

The risks associated with acupuncture are viewed as minimal risk. Although we have assessed the proposed study as one of minimal risk, the potential exists for anticipated and/or unanticipated adverse events, serious or otherwise, to occur since it is not possible to predict with certainty the absolute risk of this procedure in this context.

Therefore, we provide a plan for monitoring the safety of the participants in the study as

follows:

Attribution of Adverse Events

Adverse events will be monitored for each subject participating in the study and attributed to the study procedures / design by the principal investigator according to the following categories:

- Definite: Adverse event is clearly related to investigational procedures(s)/agent(s)
- Probable: Adverse event is likely related to investigational procedures(s)/agent(s)
- Possible: Adverse event may be related to investigational procedures(s)/agent(s)
- Unlikely: Adverse event is likely not to be related to the investigational procedures(s)/agent(s)
- Unrelated: Adverse event is clearly not related to investigational procedures(s)/agent(s)

Grading Adverse Events

The following scale will be used in grading the severity of adverse events noted during the study:

1. Mild adverse event
2. Moderate adverse event
3. Severe adverse event

An adverse event is considered serious if it results in ANY of the following outcomes:

- Death
- A life-threatening adverse event
- An adverse event that results in inpatient hospitalization or prolongation of existing hospitalization
- A persistent or significant incapacity or substantial disruption of the ability to conduct normal life functions
- A congenital anomaly/birth defect
- Important Medical Events (IME) that may not result in death, be life threatening, or require hospitalization may be considered serious when, based upon medical judgment, they may jeopardize the patient or subject and may require medical or surgical intervention to prevent one of the outcomes listed in this definition

Note: hospital admission for a planned procedure/disease treatment is not considered an SAE. Additionally, grade 1-3 events from the following list of protocol complications will be considered expected on study and not reportable as SAEs: bleeding, discomfort, and residual pain at the insertion points. These will be tracked separately through the protocol data collection sheets.

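### The plan defines its adverse event set differently in 8.0 than in 1.0, 9.2 and 10.3, and does not say which set is the analysed safety outcome

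*Combined protocol and SAP*

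**What the plan says.** Four places in the combined protocol and SAP bear on which adverse events are collected.

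- **Section 8.0 (Outcome Evaluation):** "Adverse events related to the interventions will be recorded throughout enrollment". The bullet carries a relatedness condition.
- **Section 9.2 (Data and Safety Monitoring):** "Adverse events, related or unrelated to the acupuncture procedure, will be reported, attributed, and graded for severity by the clinician and documented in EPIC". There is no relatedness condition.
- **Section 10.3 (SAE Reporting):** "Adverse events will be monitored for each subject participating in the study and attributed to the study procedures / design by the principal investigator". The attribution scale has five levels, from definite to unrelated.
- **Section 1.0 (Objectives):** safety is a secondary objective, "To determine the safety of preoperative acupuncture by recording complications throughout hospital length of stay". Again there is no relatedness condition.

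Section 10.2 adds two statements about timing: "Adverse events will be monitored during and after acupuncture and throughout admission" and "Emergency visits and hospital readmissions stated in EPIC will be recorded up to thirty days postoperatively".

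On analysis, section 11.0 (Statistical Methods) says: "The primary and secondary study outcomes will be compared between groups two ways". The two ways are a t-test or Mann-Whitney test at each time point, and a mixed model for repeated outcomes. No method is named for adverse event counts. Section 3.1 describes the control arm as receiving no intervention, and the trial is open-label.

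**The concern.** The outcome section normally tells the data manager what to enter and the analyst what to tabulate. Here it names a narrower set than the safety sections do. A team could reasonably follow 8.0 for the study database and 9.2 for the medical record, since 9.2 sends events to EPIC while section 9.0 puts study data in REDCap. Events judged unrelated would then sit in the chart and stay out of the tabulated safety outcome.

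Two consequences follow if 8.0 governs and the interventions are taken to mean acupuncture. First, a patient who receives no acupuncture cannot have an event related to it, so the control column is empty by definition. Second, in the acupuncture arm an event counts only after someone who knows the allocation has judged it related. A harm that was not recognised as such would be left out of the outcome. A comparison of all-cause events by randomised arm does not depend on that judgement.

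**Working it through.** The plan states no safety sample size, control event rate or safety power, so there is no figure of its own to reproduce. The check is a comparison of the text, followed by a short calculation of what the data could show once the definition is settled.

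**Step 1. The definitions side by side**

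| Section | Relatedness condition | Who is covered | Period |
|---|---|---|---|
| 1.0 | None (complications) | Not stated | Hospital stay |
| 8.0 | Related to the interventions | Not stated | Enrolment (by 3.1, consent to 30 days after surgery) |
| 9.2 | None (related or unrelated) | Participants | Not stated |
| 10.2, adverse events | None | Not stated | During and after acupuncture, and admission |
| 10.2, emergency visits and readmissions | None | Not stated | To 30 days after surgery |
| 10.3, adverse events | None; relatedness is graded | Each subject | Not stated |

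Only 8.0 carries the condition. An attribution scale that includes an unrelated category makes sense only if unrelated events are captured, so 10.3 agrees with 9.2. No section ranks these rules or names the analysed set.

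**Step 2. The periods**

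The periods differ too. Part of 10.2 is anchored to acupuncture. SAE reporting in 10.3 starts at consent and ends 30 days after the last investigational treatment or intervention, a date that a control patient does not have. A by-arm summary needs one period that applies to both arms.

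**Step 3. The analysis**

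Section 11.0 assigns chi-square and Fisher's exact tests to patient characteristics. The methods given for outcomes suit scale or repeated data. Adverse event counts fit neither, so their summary is unspecified under every definition.

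**Step 4. What all-cause data could show at the planned size**

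Inputs: 30 per group (section 11.0; 52 / 0.90 = 57.8, rounded up to 58, with an aim of 60). The background all-cause event proportion p is an **assumption**, shown from 10% to 50%, because the documents give none.

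Approximate 95% half-width for a difference between arms, with the same p in both: 1.96 × √(2p(1 − p)/30).

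- p = 0.10: about 3 patients per arm; 1.96 × √(0.18/30) = 0.152
- p = 0.30: about 9 patients per arm; 1.96 × √(0.42/30) = 0.232
- p = 0.50: about 15 patients per arm; 1.96 × √(0.50/30) = 0.253

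Power of a two-sided Fisher's exact test at 0.05 with 30 per arm, from exact binomial enumeration at assumed rates:

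- 10% against 20%: 0.10
- 10% against 30%: 0.37
- 30% against 40%: 0.08
- 30% against 50%: 0.26

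Under the broader definition both arms can contribute events and a difference can be estimated, but only to within roughly 15 to 25 percentage points. That is a descriptive comparison.

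**The case against.** The strongest reply is that one loosely worded bullet is being set against several clear statements. Section 8.0 says that related events will be recorded; it does not say that unrelated ones are excluded. The term for the interventions is plural and undefined, and section 7.0 uses the same word in a heading that covers both arms. Sections 9.2, 10.2 and 10.3 all produce control-arm data. The 8.0 bullet, unlike most of its neighbours, promises no comparison between groups, so descriptive reporting may have been intended all along.

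Most of this stands, and it rules out three stronger readings that a reader might infer.

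- **That the safety outcome has no comparator.** The documents do not support this for the plan as a whole. Unrelated events go into EPIC under 9.2, events are monitored for each subject under 10.3, and emergency visits and readmissions are recorded to 30 days without a filter under 10.2.
- **That unrelated events are lost.** They could be missing from the tabulated outcome, but they remain in EPIC, which is already the source for several study outcomes, and can be recovered.
- **That the 6% rate in 10.2 measures the defect.** It gives 30 × 0.06 = 1.8 expected events in the acupuncture arm against none in controls. But that rate counts acupuncture-related events, mostly bleeding, discomfort and pain at insertion points. Controls cannot have these under any recording rule, so the contrast would be the same after the fix.

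The reply does not settle which set is analysed. That several sections favour all-cause capture is a good reason to align 8.0 with them, but it does not tell the analyst that 8.0 is superseded. The lack of any stated summary for adverse events also remains.

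**Conclusion.** The point holds as an internal inconsistency of minor severity. Section 8.0 and sections 1.0, 9.2 and 10.3 define different adverse event sets, and the analysed safety outcome is not identified. The consequence for the control arm, that it can contribute no events, is conditional on two assumptions: that 8.0 governs the outcome, and that the interventions mean acupuncture. The second is the natural reading given a no-intervention control, but it is not stated.

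How many events the narrower definition would leave out cannot be computed from the documents. Removing the inconsistency would not turn safety into a powered comparison. Its value is that inclusion would no longer rest on an open-label attribution, and that both arms would be described on the same basis.

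**What to change.** Amend the adverse event bullet in 8.0 to agree with 9.2 and 10.3. Possible wording: All adverse events, regardless of attribution, will be recorded in both groups over the same period; relatedness is recorded as an attribute of the event and does not determine inclusion. State that period in terms that apply to both arms, for example from consent to 30 days after surgery, which is the follow-up already given in 3.1.

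Add a sentence to 11.0:

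- All-cause adverse events are summarised by randomised arm, as the number and proportion of patients with at least one event and the number of events, with a 95% confidence interval for the difference in proportions.
- Insertion-point and acupuncture-related events are reported descriptively for the acupuncture arm only.
- The safety comparison is descriptive.

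The cost is a wording amendment, plus abstraction to REDCap of unrelated events that 9.2 already requires in EPIC, for up to 60 patients. For patients already enrolled this can be done from the chart.
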